4. During the 14-day data collection period, data from the EMA will be collected using EMA software platform on a personal smartphone (iOS or Android) and EMA software platform.⁷³ Each morning, participants will receive an EMA survey concerning asthma symptoms and a reminder to use their spirometer. Additionally, EMA surveys addressing disinfectant use, asthma symptoms, and spirometry will occur randomly twice/day (6am – 10pm) or tailored for those working off hours (Appendix).
5. A custom interface between the EMA platform and the Awair indoor air quality monitor will alert participants when levels of indoor VOCs or particulates are detected outside the optimal range (Table 1). The air quality monitor will communicate with the EMA platform using publicly available application programming interface (api). Upon notification from the Awair, the EMA will signal the participant to complete a brief survey on disinfectant use/air particulate exposure (depending on the alert), current asthma symptoms, and proximity to the Awair (Appendix). The EMA will then direct participants to use the spirometer. Participants experiencing symptoms will be guided to follow their asthma action plan/provider instructions.
6. Thirty minutes after VOC/PM_{2.5} notification, a second EMA notification will be sent for participants to complete a survey on mitigation strategies, respiratory outcomes, and spirometry use if not already completed (Figure 4).
7. Research personnel will monitor use of these devices/apps and contact participants if a 24-hour gap in data is noted to address concerns and determine acceptability. Research team members will check-in with each participant at about the 7-day mark to address technical concerns and ease of use.

8. At the end of the 14 days, participants will complete a short acceptability, appropriateness, and feasibility REDCap survey. A random sample of 20 participants will be interviewed to provide further insights.
9. Participants will be asked to return the Awair in the provided mailer. The Awair will be fully disinfected per manufacturer's directions. Participants will keep the Zephyr_x spirometer as an incentive.

Baseline Measures

The following measures will be administered at baseline via REDCap:

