1. *Adult Asthma History* includes 5 items adapted from the Behavioral Risk Factor Surveillance System Survey.⁷⁴ Four items address participants' recent contact with healthcare professionals for asthma since COVID-19. The final item addresses changes in routine work/activities due to asthma since COVID-19.
2. *Asthma Control Test (ACT)*. The ACT includes 5 items addressing: asthma symptoms, use of rescue medications, and effect of asthma on daily functioning. Responses are summed for total ACT score.^{75,76}
3. *Airborne Exposures*. The 7 items from the PROMISSM Pool V1.0 Dyspnea Airborne Exposure address airborne allergens, pollutants, smoke, pets, and use of pesticides using Yes:No response options.⁷⁷
4. *Adult Asthma Adherence Questionnaire*,TM includes 5 items on following their prescribed asthma medication plan and barriers to following that plan.⁷⁸
5. *Health and Demographics* includes items such as self-rated physical health, comorbidities, height/weight, age, education, ZIP code, smoking status, and COVID-19 prevention practices, and COVID-19 exposure/infection status.
6. *Home Environmental Exposure* data will be gathered including home type, # of occupants, vacuum with HEPA filter, cleaning practices, cleaning products, air filter, heating, ventilation, smoke exposures, hand washing practices, pests, hobbies, odors, indoor plants, printers, flooring, and stove type.^{79,80}

We will also measure the following psychometrically valid measures as potential confounders:

7. *Emotional Distress-Anxiety and Depression PROMIS Short Forms 4a* assess anxiety and depression levels within the last 7 days (4 items). Higher scores indicate higher severity of anxiety or depression.^{81,82}
8. *Emotional Support*, PROMIS_SF_V2 Short Form 4A measures perceived feelings of support, being cared for and valued (4 items).⁸³ Higher score indicating a higher perceived emotional support.
9. *Perceived stress scale* includes 4 items measuring the degree to which situations in one's life are appraised as stressful.⁸⁴⁻⁸⁶ Higher scores indicate an increased level of perceived stress.

EMA survey items (See Appendix).

- *Asthma symptoms* (trouble breathing, wheezing, coughing, other symptoms [Yes:No]) assessed each time participants are asked to complete an EMA survey.
- *Random EMA surveys (twice/day)* assess use of disinfectants/cleaners in last 2 hours (Yes:No) if Yes, the type, brand, and asthma symptoms are queried.

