- *EMA survey triggered by VOCs/PM_{2.5} greater than optimal range as detected by the Awair* will query asthma symptoms, lists of probable sources of elevated VOCs or PM_{2.5}.
- *EMA survey 30-minutes after Awair air quality notification* queries mitigation strategies used (from lists) and asthma symptoms.
- *Home spirometer use* (Yes:No) queried in each EMA survey

Home spirometer. FEV₁% predicted– a standard metric of lung function for those with asthma.

Seven-Day check-in. Open-ended questions to identify any trouble-shooting areas, determine if adjustments need to be made, and assess ease of use of the app/devices. Interactions will be recorded and reviewed by the research team for patterns and to identify any adjustments that are needed.

Participant feasibility assessment. At the end of the 14-day data collection period, participants will be asked to respond to a short REDCap survey assessing acceptability, appropriateness, and feasibility of the indoor air quality monitor, EMA notifications, and the home spirometer with response ranging from 1=completely disagree to 5=completely agree. A random sample of 20 participants will be interviewed to further explore these factors using open-ended questions such as "Tell us what you liked/didn't like about the indoor air quality monitor", "Describe the strengths/concerns about the survey you received about your home indoor air quality".

Data Analysis

Each day of observation will be divided into four 4-hour periods between 6 a.m. and 10 p.m. Data from a given period will be considered as follows:

1. Period specific data from all event-contingent EMA prompts [prompts triggered by high indoor air VOC/PM_{2.5} readings] will be analyzed. If multiple event-contingent prompts were answered, data will be averaged across all event-contingent prompts during that period.
2. Data from all answered baseline and random [signal-contingent] EMA prompts will be considered.

Aim 1. For this aim, we will assess:

1. Compliance with the EMA prompts as indicated by the frequency of responses to prompts, specifically:
 - a. # of responses (complete:incomplete)/number of prompts
 - b. # times spirometer used/number of prompts
 - c. # times environment modified/number of event-contingent prompts
2. Compliance as described in 1a-1c by 4-hr each period.

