We will also assess the duration the indoor air quality monitor is used by each participant. The quantitative participant feasibility assessment of acceptability, appropriateness, and feasibility will be analyzed descriptively. In addition, we will examine differences in use/acceptance by participant characteristics (e.g., age, asthma symptoms, overall health, education, etc). Qualitative interview data will be transcribed, uploaded into Dedoose qualitative analysis software for content analysis.

Aim 2a: We will collect baseline data on the current frequency and degree of disinfectants/cleaners and exposure to environmental triggers (e.g., secondhand smoke). We will capture real-time self-reported data on disinfectant use throughout the study period. We will determine the prevalence of disinfectant/cleaner use and frequency (% EMA prompts at which disinfectant/cleaner use is reported). We will obtain data from the Awair dashboard to determine the number of times VOCs and PM_{2.5} levels exceed optimal levels, average daily levels, average levels per time period, and fluctuations in VOC and PM_{2.5}. We will identify possible environmental triggers that contribute to high levels of VOCs and PM_{2.5} leading to event-contingent prompts.

[figure not shown]
Aim 2b: We will determine baseline level of asthma control as measured by the ACT. We will use EMA to determine the level of asthma control over the study period as indicated by (a) asthma symptoms reported at each prompt and over the 14 days; (b) number of time-periods during which an EMA prompt is sent and participants report asthma symptoms; and (c) lung function as measured by FEV₁% predicted at each prompt. Asthma control will also be evaluated using EMA by exploring differences in variability in lung function.

Aim 3: Data collected using the EMA approach are multilevel with time windows (level 1) nested with individuals (level 2). The exposure variables will include: (1) Baseline self-reported use and frequency of disinfectant/cleaner use and PM_{2.5} exposures; (2) Number of times VOC and PM_{2.5} levels exceed the threshold for the optimal readings per week; and (3) Average scores of VOC and PM_{2.5} levels in the time windows considered in the analysis. The outcome variables we will consider include occurrence of any asthma symptoms, inhaler use, and FEV₁% predicted (within 30 minutes of each EMA prompt).

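### Two rules for the random EMA survey conflict; programmed from the second, the survey would record no symptoms at any random prompt where recent disinfectant use is answered No

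*Combined protocol and SAP*

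**What the plan says.** The combined protocol and SAP describes the symptom items in several places:

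- **EMA survey items, asthma symptoms bullet.** Symptoms are "assessed each time participants are asked to complete an EMA survey". No survey type is excepted.
- **EMA survey items, random surveys bullet.** These surveys "assess use of disinfectants/cleaners in last 2 hours (Yes:No) if Yes, the type, brand, and asthma symptoms are queried". Symptoms stand in the same list as type and brand, after the condition. Nothing is described for a No answer.
- **Procedures, step 4.** "EMA surveys addressing disinfectant use, asthma symptoms, and spirometry will occur randomly twice/day". Here symptoms are part of the random survey without a condition. The same step adds a daily survey: "Each morning, participants will receive an EMA survey concerning asthma symptoms and a reminder to use their spirometer".
- **Data Analysis.** All answered random prompts are to be considered. Aim 2b uses "asthma symptoms reported at each prompt and over the 14 days" and also counts the time periods in which a prompt is sent and symptoms are reported. Aim 3 takes the occurrence of any symptom as one outcome of the multilevel models.

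The survey items heading and Procedures step 4 both refer to an Appendix, which is not in the text available for this review.

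**The concern.** Two programmers working from adjacent bullets would build different instruments. One would ask symptoms at all random prompts. The other would ask them only when the participant has just reported using a disinfectant or cleaner. In the second instrument, whether the outcome is observed depends on reported exposure.

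Three things would be at stake:

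- **Aim 2b.** The random-prompt part of the symptom description would cover post-use moments only. The count of symptomatic time periods would also be affected. A period whose only prompt was a random one answered No would add nothing to the count because nobody asked, and it would look the same as a symptom-free period.
- **Aim 3.** The symptom outcome would be missing in relation to exposure. The protocol reports that the monitor detects higher VOC levels when disinfectants are used, and average VOC per time window is a listed exposure. The two-hour use item is not among the listed exposures or covariates, so the model as written would not account for this missingness.
- **Momentary contrast.** No comparison of symptoms with and without recent use could be drawn from the random prompts, because one arm of it would be empty.

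**Working it through.** The plan states no prompt count or expected share of Yes answers, so there is no figure to reproduce.

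**Step 1: which surveys the conflict touches.** Only the random survey carries the use condition. The morning survey, the alert-triggered survey and the 30-minute follow-up ask symptoms (the follow-up is also described as asking respiratory outcomes) whatever the disinfectant use.

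**Step 2: scheduled prompts.** Inputs are 50 participants (Sample), 14 days (Procedures, step 3) and two random surveys plus one morning survey a day (Procedures, step 4). Full enrolment and full response are assumed.

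- Random: 50 × 14 × 2 = 1,400, or 28 per person.
- Morning: 50 × 14 = 700, or 14 per person.

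**Step 3: share of random prompts answered No.** The look-back is 2 hours and the prompting window 16 hours (6 a.m. to 10 p.m.). The entry criterion is at least 5 uses a week; the higher rates below are assumptions. If uses fall inside the window and their look-backs do not overlap, then

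P(Yes) = (uses per week / 7) × (2 / 16).

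| Uses per week | P(Yes) | Random prompts without symptoms |
|---|---|---|
| 5 | 5/7 × 0.125 = 0.089 | 1,400 × 0.911 = 1,275 (91%) |
| 14 | 2 × 0.125 = 0.25 | 1,400 × 0.75 = 1,050 (75%) |
| 28 | 4 × 0.125 = 0.50 | 1,400 × 0.50 = 700 (50%) |

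If uses instead occur at random and may overlap, P(Yes) = 1 − exp(−expected uses in 2 hours). That gives 8.5% at 5 uses a week and 22.1% at 14, so about 1,280 and 1,090 prompts lack symptoms. Overlap makes the loss slightly larger.

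**Step 4: effect on the random-prompt symptom level.** Suppose symptoms are present at 40% of moments after use and 20% otherwise (both assumed). The true level over all random prompts is P(Yes) × 0.40 + (1 − P(Yes)) × 0.20:

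- P(Yes) = 0.10: 0.04 + 0.18 = 0.22
- P(Yes) = 0.50: 0.20 + 0.10 = 0.30

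Under the branch the observed level is 0.40 in both cases. If symptoms were unrelated to use, say 20% in both states, the level would be unbiased but the data would still be lost.

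**Step 5: what the morning survey can replace.** Each day has four 4-hour periods, so 4 × 14 = 56 per person. If each morning survey falls in one of them, it covers at most 14 of 56. Under the branch, symptoms in the other periods would be recorded only after an alert or reported use. Low-exposure symptom data would then come mostly from mornings, mixing exposure with time of day.

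**The case against.** The strongest reply is that the plan already says what it means. The general rule, Procedures step 4 and Aim 2b all imply that symptoms are asked at every prompt. The one sentence against them can be read loosely: type and brand if Yes, symptoms as always. The Appendix may settle it. This stands to the extent that the sentence may well be a drafting fault, and nobody can say from this text that the branch exists in the instrument. It does not remove the contradiction, since no section in hand resolves it.

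Some stronger inferences are tempting, and the documents do not support them:

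- *That the whole 14-day symptom level would rest on moments after cleaning.* This is true of random prompts only. The 700 scheduled morning surveys and the alert and follow-up surveys remain, and Aim 2b also uses the baseline ACT and FEV₁% predicted.
- *That Aim 3 would lose its main comparison.* The listed exposures are baseline self-reported use and PM2.5 exposures, weekly exceedance counts, and average VOC and PM2.5 levels. The two-hour item is not among them. A No answer also means only that no use was reported; VOC or PM2.5 may still be raised.
- *That a false association would be built in by storing skipped items as No.* Nothing in the plan says skips would be coded that way. It is a risk to rule out.

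The study is also a feasibility study with exploratory associations, which limits the consequences for inference. It does not make symptoms that were never asked recoverable.

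**Conclusion.** The point holds in conditional form. The plan gives conflicting rules for the random survey, and one of them, followed literally, leaves the symptom outcome unrecorded at every random prompt answered No. The size is 700 to 1,275 of 1,400 scheduled random prompts (50% to 91%). It rests on full enrolment and response, assumed rates of 28 down to 5 uses a week, and uses spread without overlap over a 16-hour day. Only the 5 comes from the plan, and it is an entry minimum. The direction does not depend on the rate.

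A reader might conclude that the plan specifies the branch as its design. The documents do not support that: they conflict, and most of the relevant text favours asking symptoms every time.

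**What to change.** State in the random-survey bullet that the symptom items are asked at every random survey whatever the answer on disinfectant use, and confine the Yes branch to product type and brand. Check the Appendix and the programmed survey against that wording.

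If any data were collected under the branch, set only the unasked symptom items to missing, never to No. Keep the spirometry and other answers from those prompts: FEV₁% predicted is an outcome in Aims 2b and 3, and dropping the No prompts whole would discard valid data while leaving the selection in place. Report random-prompt symptoms from that phase as post-use data only.

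The cost is one sentence in the plan, at most one line of survey logic, and four Yes/No items shown at each random prompt.

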EMA is a survey approach which uses repeated sampling of participants to capture behaviors and experiences in a real time context. This methodological approach maintains the ecological validity of reported behaviors and decreases the impact of recall bias as surveys are sent periodically to participants through electronic devices.⁶¹ EMA is particularly useful when trying to understand the context around symptoms or behaviors. Available literature that combines the EMA methodology with asthma research focuses primarily on asthma-related outcomes such as symptoms, control, quality of life, history, and medication adherence and their relationship with stress (perceived stress, mood, hassles, social support).⁶²⁻⁶⁴ None of the published literature to date pairs EMA with indoor air quality and asthma symptoms. The ability to timestamp behaviors, events, experiences, whether they present a positive or negative health impact, is valuable when seeking to understand the complexity of multiple risk factors and multiple environmental and behavioral interactions.

Exposure	Sensor	Range/ Accuracy	Optimal range
VOCs	Multi-pixel metal oxide semiconductor gas sensor	0-60,000 ppb/ $\pm 10\%$	<333ppb
PM _{2.5}	Laser-based light scattering particle sensor	0-1,000 $\mu\text{g}/\text{m}^3$ / $\pm 15\mu\text{g}/\text{m}^3$ or 15%	<15 $\mu\text{g}/\text{m}^3$

Awair Omni Indoor Air Quality Monitor® continuously monitors about 1,000 square feet of indoor air for 7 air quality factors: total VOC, PM_{2.5}, temperature, humidity, CO₂, ambient light, and ambient noise. This feasibility study will only focus on VOCs and PM_{2.5} levels (Table 1). The Awair Omni measures about 4"X4"X1.3", is wi-fi and Bluetooth enabled, plugs into a standard AC outlet, and includes an 8-hour battery back-up. An air quality reading is taken every 10 seconds and real-time data are uploaded to a dashboard accessed only by research personnel. The display on the Awair Omni will be limited to VOCs and PM_{2.5} data. Our preliminary work with Awair indoor air quality monitors indicates that increased VOC levels are detected when disinfectants are used and increased PM_{2.5} levels are detected when vacuuming without a

[figure not shown]
[figure not shown]
vacuum cleaner.

HEPA filter. The Awair proprietary dashboard provides secure communication between the Awair Omni and its dashboard. Data will be exported from the dashboard to a .CSV file.⁶⁵⁻⁷¹

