Zephyr_x Spirometer⁷² system allows for laboratory quality pulmonary function tests (PFTs) at home (FVS-forced vital capacity, FEV₁-forced expiratory volume in 1 second, FEV₁/FVC, flow-volume loop). The system consists of an FDA approved handheld Bluetooth spirometer (MIR Spirobank Smart), and a mobile application that works on a smartphone or tablet device. The MIR Spirobank bank measures 49x109x21 mm and weighs 60.7 g. Participants share PFT results through their app and researcher team members will access a HIPAA compliant portal to view participants' PFT results in real time. An in-App video coaching feature guides the participant through the PFT maneuver. Each maneuver conducted by the participant creates a time and date stamped American Thoracic Society standard PFT report accessible through the portal. Data will be exported from the dashboard to a .CSV file.

Procedures (Figure 3)

1. Randomly selected individuals from the CGAS study who meet eligibility criteria will be invited to participate in the current study. Those interested will be directed to a REDCap link to complete an E-consent form and baseline questionnaire.
2. An Awair Indoor Air Quality Monitor and a Zephyr_x Spirometer will be mailed to each participant along with a quick start guide, written instructions with a link to an instructional video, and research team contact information. Once received, a research team member will conduct a live chat with each participant to enable the devices, download apps (EMA, Zephyr_x), setup and test the devices and apps, review the protocol, and address questions. Participants will be instructed to place the portable Awair air quality monitor in the room where they spend the most time during the day and at night where they sleep.
3. A 3-day run-in period will be completed during which the participants will become familiar with the devices and troubleshoot issues (Awair requires 24-48 hours to calibrate VOC sensors). Study personnel will be available to answer questions/address technical issues. After the run-in period, a research team member will contact the participant to launch the 14-day data collection period.

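### No analysis period covers the night, so morning outcomes have no exposure variable for the preceding night, and any night alerts would mix sleep with non-response in overall compliance

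*Combined protocol and SAP*

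**What the plan says.** **Monitoring.** The Awair paragraph under Data collection methods says "An air quality reading is taken every 10 seconds". Procedures, step 2, has participants place the monitor "in the room where they spend the most time during the day and at night where they sleep". Overnight readings from the sleeping room are therefore collected by design.

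**Prompts.** Procedures, step 4, schedules a morning prompt ("Each morning, participants will receive an EMA survey concerning asthma symptoms") with a spirometer reminder. It also schedules random surveys that "will occur randomly twice/day (6am – 10pm) or tailored for those working off hours". Under step 5 the interface "will alert participants when levels of indoor VOCs or particulates are detected outside the optimal range", and step 6 adds "Thirty minutes after VOC/PM_{2.5} notification, a second EMA notification will be sent". Steps 5 and 6 give no hours.

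**Analysis.** Data Analysis says "Each day of observation will be divided into four 4-hour periods between 6 a.m. and 10 p.m". Item 1 there handles alert-triggered responses period by period. Item 2 takes in every answered baseline and random prompt. Aim 1 items 1a and 1b divide by all prompts, and 1c divides by the alert-triggered ones, none with an hour limit. Aim 1 item 2 repeats the three ratios by 4-hour period.

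**Exposure summaries.** Aim 2a lists exceedance counts, daily averages, per-period averages and fluctuations. Aim 3 lists three kinds of exposure: baseline self-report, weekly exceedance counts, and average levels within the analysis windows.

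**The concern.** There are two separate problems, and they affect different measures.

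**Aim 3.** Of the three exposures, the first is fixed at baseline and the second gives about two values per person in 14 days. Only the third varies from window to window, and it stops at 10 p.m. Each morning's symptoms and FEV1% predicted follow a night in the monitored bedroom, but the models hold no variable for that night. The question is within the protocol's own scope: the Significance section cites a 12-week study that set nighttime particulates against daily asthma outcomes (it found no consistent relationship).

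**Aim 1.** If alerts go out at night, a sleeping participant's missed prompts count in the overall ratios exactly as a refusal would. The by-period table has no night cell, so it cannot show the cause of the shortfall. Feasibility is the first aim, and the results are meant to inform a later powered study. A compliance figure that cannot separate sleep from unwillingness is a poor guide for that.

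A smaller point follows from step 4: prompt times may be moved for off-hours workers, but the analysis periods stay fixed to the clock.

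**Working it through.** **Coverage**

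- The plan's own figure: 4 periods × 4 h = 16 h, which matches 6 a.m. to 10 p.m. (22 − 6 = 16).
- Time in no period: 24 − 16 = 8 h a day; 8/24 = 33.3%.
- Over 14 days: 14 × 8 = 112 of 14 × 24 = 336 hours per participant.
- At one reading per 10 s (360 an hour): 112 × 360 = 40,320 of 336 × 360 = 120,960 readings.

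**Which measures the gap reaches**

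| Measure | Tied to the four periods? | Night content |
|---|---|---|
| Aim 2a exceedance counts, daily averages | No | May be included; not stated |
| Aim 2a per-period averages | Yes | Excluded |
| Aim 3 weekly exceedance count | No | May be included; not stated |
| Aim 3 average level in the windows | Yes | Excluded |
| Aim 1 ratios 1a–1c, overall | No | Any night prompts are in the denominator |
| Aim 1 ratios by 4-hour period | Yes | Excluded; no night cell |

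**Effect on pooled compliance (1a)**

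From the documents: 3 scheduled prompts a day (1 morning, 2 random), 2 prompts per alert (initial and 30-minute), 14 days. Assumed, because the documents give no rates: 1 daytime alert a day, 80% daytime response, and night response of 0% or 20%.

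Compliance = (day prompts × day response + night prompts × night response) / all prompts.

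- Day prompts: 14 × (3 + 2 × 1) = 70, of which 0.80 × 70 = 56 are answered.
- Night prompts: 14 × 2 × (night alerts per night).

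| Night alerts per night | Night prompts | Compliance, 0% night response | Compliance, 20% night response |
|---|---|---|---|
| 0 | 0 | 56/70 = 80.0% | 80.0% |
| 0.25 | 7 | 56/77 = 72.7% | 57.4/77 = 74.5% |
| 0.5 | 14 | 56/84 = 66.7% | 58.8/84 = 70.0% |
| 1 | 28 | 56/98 = 57.1% | 61.6/98 = 62.9% |
| 2 | 56 | 56/126 = 44.4% | 67.2/126 = 53.3% |

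Sensitivity to the daytime alert rate, at 1 night alert per night and 0% night response: with no daytime alerts, 33.6/70 = 48.0%; with 2 a day, 78.4/126 = 62.2%.

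Ratio 1c has no scheduled prompts in its denominator to dilute the effect. With 1 daytime alert a day and no environment changes made at night, it becomes 28/(28 + 7) = 80% of its daytime value at 0.25 night alerts per night, and 28/(28 + 28) = 50% at 1.

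**The case against.** The strongest reply is that the plan is less closed than it looks. A reader might infer several stronger claims that the documents do not support.

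- **That overnight data are discarded or never linked to outcomes.** The daily averages and weekly exceedance counts are not limited to the four periods, and the weekly count is an Aim 3 exposure. Night readings can enter the models by that route. This stands. But a weekly count cannot connect one night to the next morning.
- **That night alerts cannot be answered.** Some participants may be awake, and off-hours workers are expressly foreseen. The Appendix and Figure 4, to which the procedures refer, are not in the text available and might contain a quiet-hours rule. This also stands. Such a rule would settle the compliance question but not the exposure gap.
- **That alert compliance would drop to 53% or 47%** (0.80 × 16/24 or 0.70 × 16/24). Neither figure matches a planned measure: 1a pools all prompts, and 1c counts environment changes. Both figures also need alerts spread evenly over 24 hours and no night response. Many sources the protocol names, such as disinfecting, vacuuming and cooking, are waking activities.
- **That off-hours workers lose data.** Item 2 of Data Analysis considers every answered baseline and random prompt. What is undefined is only how their prompts map to the fixed periods.
- **That night hours are certainly spent beside the monitor.** That depends on participants moving it, and adherence is unknown.

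It can also be said that data cannot be both excluded and harmful to compliance. For any one measure that is right. Here the exclusion affects the window-based exposures, and the dilution affects the overall ratios. By-period compliance is not lowered.

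Finally, Aim 3 is exploratory and the study is a feasibility study. That limits the weight of the point, but the fix is correspondingly light.

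**Conclusion.** The point holds and should be corrected before analysis; it does not threaten the study. The exposure gap follows directly from the text and needs no assumption about rates: 8 of 24 hours fall in no window, and those hours come just before each morning's outcomes.

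The compliance effect is conditional. It arises only if alerts are sent at night and the overall ratios keep those prompts in their denominators, as their wording implies. Its size cannot be known from the documents. In the illustration, between 0.25 and 1 night alert per night takes pooled compliance from 80% to between about 73% and 57% with no night response, or between about 75% and 63% with 20% night response.

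**What to change.** 1. Add a 10 p.m.–6 a.m. window, or one defined by each participant's own sleep period. Use its mean and peak VOC and PM2.5 as a lagged exposure for the morning survey and FEV1% predicted in the Aim 3 models.
2. Report 1a–1c, and the response rate to alert prompts alone, separately for waking and sleep hours, next to the overall figures.
3. For participants with tailored prompt times, define the periods on their own waking schedule.
4. State whether alerts are sent between 10 p.m. and 6 a.m., and which Aim 2a and Aim 3 summaries use 24-hour data.

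Items 1 to 3 use time-stamped data that the design already collects, so they can be done after data collection. The cost is extra derivation and one more exploratory exposure, to be labelled as such. No change to night alert delivery is proposed: step 5 also guides participants with symptoms, so delivery is not purely a data setting.
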